Experimental Tobacco Marketplace sessions (4 sessions, approximately 30-60 minutes each). Each participant will be initially randomly assigned to one of the following concentration groups: 0.4 mg/g, 1.4 mg/g, 2.5 mg/g, 5.6 mg/g, and 17.4 mg/g. Random assignment will be double blind, such that the participant and any research staff directly interacting with the participant will not be aware of the assigned cigarette concentration (but as indicated previously, an algorithm will then be used to assign participants to strive for equally balanced groups on demographic and cigarette measures). However, as mentioned in the assessment sessions, participants will be informed that some of the cigarettes they will be using during the course of the study may have reduced-nicotine. In the purchasing scenario, labels will differentiate the experimental cigarettes from the conventional cigarettes. For reference, conventional cigarettes sold in stores range from ~16-19 nicotine mg/g (Malson et al., 2001). During these four sessions, participants will sit in front of a computer and respond to an online marketplace where they will be able to "purchase" a variety of nicotine products (e.g., conventional cigarettes, nicotine gum, snus, electronic cigarettes). Importantly, the marketplace interface mimics what participants might encounter if they shopped online for these products. In order to obtain the behavioral economic measures described earlier (e.g., demand intensity, substitutability, complementarity), in each session participants will complete a series of purchasing scenarios where the price of cigarettes (experimental and/or conventional) is manipulated (approximately 6 prices) and all other nicotine products remain at a constant price. Participants will be given an income equal to five days worth of their typical expenditure on cigarettes and will be asked to make purchases for the following five days. They will be able to keep the remaining balance from the income. At the end of each marketplace session, the participant will receive the nicotine products they purchased from one randomly selected pricing scenario. After at least approximately five days following each marketplace condition, participants will return to purchase more cigarettes and report the use of experimenter provided and non-experimenter provided tobacco/nicotine products, with the ability to return any unused experimenter provided products for a refund. At the end of the fourth laboratory marketplace session, participants will complete a brief questionnaire (Stages of Change Readiness and Treatment Eagerness Scale-S; Miller & Tonigan, 1996; Park et al., 2012).

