
The four marketplace sessions (presented in a counterbalanced order) will consist of the following conditions:

1. Price of conventional cigarettes will be manipulated with other nicotine products at a constant price
2. Price of experimental cigarettes will be manipulated with no other products available
3. Price of experimental cigarettes will be manipulated with other nicotine products at a constant price
4. A blend of 1 and 3 such that price of conventional cigarettes and experimental cigarettes will be simultaneously available (one will be manipulated while the other is held constant and vice versa) with other nicotine products at a constant price

At the last in-lab Experimental Tobacco Marketplace session participants may be recruited for an addendum to this study, which includes two additional sessions (described below). If the participant agrees and is a female, she may be retested for pregnancy at this time. Participants will only be approached and recruited contingent upon approval by the FDA Center for Tobacco Products for these additional sessions.

Post-marketplace Sampling (1 session; approximately 15-30 minutes): After at least approximately five days following the fourth marketplace session, participants may return to the laboratory for the ability to return any unused experimenter provided products for a refund and report the number of tobacco products used since the previous session. During this session, all participants, regardless of assigned investigational cigarette concentration, will be provided five-days' worth each of the "high" (17.4 mg/g) and "low" (0.4 mg/g) investigational cigarette. In addition to the "Investigational Tobacco Product" label, these cigarettes will be labeled with arbitrary codes e.g., "A" and "B" (randomized across participants as to which concentration the code reflects); for subsequent tasks, participants will be told that cigarette "C" refers to the investigational cigarette they were assigned to at the onset of the study. Participants will be told to use only these cigarettes for the following five days.

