In this experiment, we will ascertain the impact of reduced-nicotine on consumption of multiple products in the complex tobacco marketplace. We will assess control conditions and two regulatory environments directly relevant to the introduction of reduced-nicotine cigarettes to the current tobacco marketplace.

Participants

174 current cigarette smokers will be recruited from the community surrounding Roanoke, VA with the same eligibility criteria as in Experiment 1. We expect that approximately 14% of these participants will drop-out prior to completion based on a recent experiment with a similar population and time commitment, leaving 150 participants (30 in each of five dose groups) with complete data (chosen based on a power analysis below).

Procedure

Each participant will be randomly assigned to a dose group matching one of the reduced-nicotine cigarettes from Experiment 1 (0.4 mg/g, 1.4 mg/g, 2.5 mg/g, 5.6 mg/g, and 17.4 mg/g). Random assignment will be double blind, such that the participant and any research staff directly interacting with the participant will not be aware of the assigned cigarette dose. After granting informed consent, participants will complete an assessment session, a sampling period to familiarize them with their assigned cigarette dose, and four Experimental Tobacco Marketplace sessions. Participants will not be asked to be abstinent from nicotine prior to experimental sessions. The participants who enroll into the experiments and either complete or drop out will be illustrated according to the revised Consolidated Standards of Reporting Trials (CONSORT) statement (Moher, et al., 2001).

Assessment Session. The first session will be an assessment session to collect information from participants on substance use patterns and severity, as well as the results of behavioral and cognitive tasks that we think may inform or complement the results from the main study. The same set of assessments as in Experiment 1 will be used (**Table 1**).

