For Aim 2, we request a total sample size of n=150 completed participants (30 per dose). The goal of Aim 2 is to analyze condition effects within each dose. To estimate an effect size for this experiment, the same paper (Johnson, et al., 2004) used in Aim 1 was used to estimate the effect of introducing reduced-nicotine cigarettes into a condition containing conventional cigarettes and an alternate commodity (nicotine gum in the previous paper), one of the main analysis types we intend to do (see below). In this paper, using a reanalysis similar to that described above, making denicotinized cigarettes available in addition to conventional cigarettes and gum reduced the substitution of nicotine gum, which was associated with an effect size of $f = 0.382$, which is near to a 'large' effect by convention (Cohen, 1992). Due to the multifaceted nature of the analyses in Aim 2, we chose a more conservative effect size of $f = 0.25$, a 'medium' effect. Using this effect size, our power analysis yielding 30 participants per dose based on a within-factors ANOVA for each individual dose, 4 repeated measures (conditions), a type 1 error rate of $\alpha = 0.05$, and 90% statistical power. Further, our tests include the statistical interaction between dose and scenario using a within-between interaction ANOVA model. With the requested sample size, we will have sufficient statistical power to detect interaction effects of $f = 0.14$, close to a 'small' effect size. Hence, we have ample statistical power to detect meaningful effects in this study. These analyses were performed in G*power version 3.1.9.2.

Data Analyses

General Demand Analysis Procedure. The nonlinear regression demand analyses to obtain subject-specific measures of intensity and elasticity are analogous to Aim 1. To satisfy the goals of Aim 2, data will be further analyzed as described below.

General Substitution Analyses Procedure. Aim 2 involves a number of comparisons of substitution among products in the four scenarios in addition to the demand-style analyses in Aim 1. To address the substitution goals we will use a modification analogous to that we've used before (Koffarnus, et al., 2015) of an equation proposed by Hursh and Roma (2013), which relates consumption of a fixed-price commodity (e.g., a non-combustible nicotine product in condition **a** of **Table 2**) as price of a primary commodity (e.g., usual brand of cigarettes in condition **a**) changes:

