$$Q = Q_{alone} * 10^{I * e^{-\beta C}}$$

In this equation, Q_{alone} represents the maximum consumption of the fixed-price commodity when the primary commodity has a price high enough to drive consumption to zero, β is the sensitivity of fixed-price commodity consumption to the price of the primary commodity, I is an interaction parameter that indicates whether the fixed-price commodity is a substitute (positive I value), complement (negative I value), or independent (I value near zero), and Q and C represent consumption of the fixed-price commodity and cost of the primary commodity, respectively, and are known from data. This equation has three parameters (Q_{alone} , I , and β) that will be estimated from experimental data using nonlinear regression. Analysis will proceed similarly as in Aim 1 with the substitution equation being fit to individual subject data to generate subject-specific estimates of maximum consumption, interaction, and sensitivity. These values will then be further analyzed to satisfy the goals of Aim 2.

Primary Analyses of Interest in Aim 2. Aim 2 involves a number of comparisons between demand characteristics (intensity and elasticity) and substitution (maximum consumption, sensitivity, interaction) across and within both doses and conditions involving three types of commodities (reduced-nicotine cigarettes, conventional cigarettes, and other non-combustible products). Within-dose statistical comparisons are briefly described in **Table 2**. Each of these effects will also be compared in larger mixed-effect models across dose with dose entered as a between-subject variable to determine the degree to which these substitution and demand effects differ by dose.

1. Compare substitution (maximum consumption, sensitivity, and interaction) of conventional cigarettes for reduced-nicotine cigarettes and vice versa in condition **d**. In separate pricing scenarios, this condition will include both conventional and reduced-nicotine cigarettes as a constant-price and modified-price commodity, allowing us to assess the degree to which the two cigarette types substitutes for one another. This analysis will inform regulators the degree to which reduced-nicotine cigarettes will, at each of the doses included here, replace conventional cigarettes in the marketplace as a functionally equivalent commodity (substitutes) or act independently in the marketplace without affecting consumption of the other cigarette (independents).

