2. This analysis will compare demand intensity and elasticity of reduced-nicotine cigarettes across conditions **b**, **c**, and **d**, informing regulators of the degree to which consumption of reduced-nicotine cigarettes at each of the doses studied here changes as a function of the other nicotine products present in the marketplace, including conventional cigarettes.
3. This analysis is analogous to analysis 2, but will compare demand intensity and elasticity of conventional cigarettes across conditions **a** and **d**, informing regulators of the degree to which consumption of conventional cigarettes is affected by the presence or absence of reduced-nicotine cigarettes in the marketplace at each reduced-nicotine dose.
4. This analysis will also compare whether cross-price elasticity parameters (maximum consumption, sensitivity, and interaction) for non-combustible products change when reduced-nicotine cigarettes are added to the current marketplace in addition to conventional cigarettes (**a** versus **d**), and when reduced-nicotine cigarettes replace conventional cigarettes in the marketplace (**a** versus **c**). These analyses will inform regulators how the introduction of reduced-nicotine cigarettes at each dose included here will affect the overall nicotine product marketplace and influence consumption of other nicotine products.
5. This analysis will compare substitution of other nicotine products for reduced-nicotine cigarettes with (condition **d**) and without (condition **c**) conventional cigarettes in the marketplace. This analysis will inform regulators how, under circumstances where reduced-nicotine cigarettes are present in the marketplace at one of the doses studied here, removal of conventional cigarettes will affect consumption of other nicotine products also present in the marketplace.

To complete the analyses in Aim 2, a random effect will be included to model any subject effect, and socio-economic and other demographic variables will be statistically screened for inclusion using model-based hypothesis tests.

Difficulties and Limitations

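### Experiment 2 counterbalances condition order, but its visible Aim 2 models have no session-position term, so drift shared across sessions would cost a little precision

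*Combined protocol and SAP*

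**What the plan says.** **Design.** The Experiment 2 protocol, section 5.1, introduces the conditions with "The four marketplace sessions (presented in a counterbalanced order" and lists four of them. The research plan calls its conditions a to d. Sessions are at least about five days apart. Between them participants use what they bought: "At the end of each marketplace session, the participant will receive the nicotine products they purchased from one randomly selected pricing scenario". Dose is a between-subject factor. After an initial random phase, "an algorithm will then be used to assign participants to strive for equally balanced groups on demographic and cigarette measures"; condition order is not among the measures named.

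**Sample size.** The research plan (Experiment 2, Participants) expects dropout, "leaving 150 participants (30 in each of five dose groups) with complete data". The Sample Size Justification states that "The goal of Aim 2 is to analyze condition effects within each dose" and bases 30 per dose on a within-factors ANOVA for each dose: four conditions, f = 0.25, alpha 0.05, 90% power. It adds that "our tests include the statistical interaction between dose and scenario using a within-between interaction ANOVA model" and gives f = 0.14 as detectable.

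**Models.** Primary Analyses of Interest in Aim 2 lists five analyses. Analysis 1 lies within condition d. Analyses 2 to 5 compare conditions (b, c and d; a and d; a and c; c and d). The section says "Each of these effects will also be compared in larger mixed-effect models across dose with dose entered as a between-subject variable" and closes with the sentence that "a random effect will be included to model any subject effect, and socio-economic and other demographic variables will be statistically screened for inclusion". No visible text for Experiment 2 names a session, period, order or sequence term.

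**The concern.** Counterbalancing spreads a session trend evenly over the conditions and so protects the condition means. It does not take the trend out of the error term; only fitting position does that. Some drift is plausible: the purchasing task is repeated over several weeks, and participants use study products between visits. The listed terms would not absorb it. The subject effect removes only each person's average level, and position is not a socio-economic or demographic variable. The covariates that Difficulties and Limitations adds for dropout are demographic or product-use differences, so they do not cover it either.

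What is at stake is power for the condition comparisons within dose, which the plan calls the goal of Aim 2, and for the dose-by-condition interaction.

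**Working it through.** **Inputs.** From the Sample Size Justification: m = 4 conditions, n = 30 per dose, N = 150, f = 0.25 within dose, f = 0.14 for the interaction, alpha 0.05. Assumed, because the documents do not state them: correlation ρ = 0.5 between repeated measures, sphericity, and a linear drift of s within-subject residual SD per session, with s from 0.05 to 0.3.

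**1. The plan's own figures.** λ = f²·n·m/(1 − ρ).
- Within dose: λ = 0.0625 × 30 × 4 / 0.5 = 15 on 3 and 87 df, power 90.4%. With n = 29, power is 89.2%, so 30 is the smallest n that reaches 90%.
- Interaction: λ = 0.0196 × 150 × 4 / 0.5 = 23.52 on 12 and 435 df, power 91.7%.

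The stated sample size reproduces.

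**2. What drift adds when position is omitted.** Centred position effects are −1.5s, −0.5s, 0.5s and 1.5s. Their sum of squares per participant is s²(2.25 + 0.25 + 0.25 + 2.25) = 5s². If order is balanced within dose, all of it goes to the residual. The residual mean square is multiplied by 1 + 30 × 5s²/87 = 1 + 1.724s². For the interaction, 150 × 5s²/435 gives the same factor. At s = 0.3 it is 1.155. Power follows from an F ratio whose denominator has noncentrality 30 × 5s² (13.5 at s = 0.3), or 150 × 5s² for the interaction (67.5).

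| s | Within-dose power | Within-dose type I | Interaction power | Interaction type I |
|---|---|---|---|---|
| 0 | 90.4% | 5.0% | 91.7% | 5.0% |
| 0.05 | 90.3% | 4.9% | 91.5% | 4.9% |
| 0.1 | 89.9% | 4.7% | 91.0% | 4.5% |
| 0.2 | 88.5% | 4.0% | 88.7% | 3.3% |
| 0.3 | 86.0% | 3.0% | 84.2% | 1.9% |

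**3. Order balanced only across all 150.** Simulation with Williams-square orders, 12,000 trials per setting, Monte Carlo error about ±0.5 point for power. For s = 0.05 / 0.1 / 0.2 / 0.3, within-dose power is 90.1 / 89.6 / 88.6 / 85.2% and interaction power 91.9 / 91.0 / 89.1 / 86.9%. Type I error stays at 4.7 to 5.3%. The loss is similar and the test is not conservative.

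**4. Comparisons closer to those planned.** No listed analysis compares all four conditions at once. Effects were therefore set to give 90% power without drift (f = 0.306 for a versus d; f = 0.272 for b, c and d). These effects are a device, not figures from the plan. Power with position omitted, at s = 0.1 / 0.2 / 0.3:

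| Comparison | Order balanced within dose | Order balanced overall only |
|---|---|---|
| a versus d, within dose | 89.7 / 88.9 / 86.9% | 89.4 / 88.2 / 86.0% |
| b, c, d, within dose | 89.3 / 88.5 / 85.9% | 89.4 / 87.9 / 85.5% |
| a versus d, by dose | 89.2 / 87.8 / 85.2% | 89.2 / 88.5 / 84.8% |
| b, c, d, by dose | 89.3 / 86.5 / 82.9% | 90.0 / 87.9 / 84.7% |

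**5. With position fitted in the across-dose model, s = 0.3.** Interaction power rises from 84.5% to 92.0% (order balanced within dose) or from 86.9% to 91.6% (balanced overall). Within-dose contrasts taken from that model rise from 87.2–89.1% to 91.0–91.9%.

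**6. Uneven sequences.** Since 30 = 7 × 4 + 2, exact four-sequence balance within a dose is impossible; the simulations used 7 or 8 per sequence. With 174 enrolled and 24 lost at random, at s = 0.3, power with position omitted was 85.7% (within dose) and 85.1% (interaction). With position fitted it was 90.0% and 92.1%.

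**The case against.** **Size.** The drift is assumed, and nothing in the documents suggests its magnitude. At 0.1 SD per session the loss is under one point. The plan also has a margin: it powers for f = 0.25 after estimating f = 0.382 from a cited study. At f = 0.382 the four-condition within-dose test keeps 99.9% power even at 0.3 SD. This stands and makes the point minor. The margin rests on one comparison in one study, however, and the plan itself chose not to rely on it.

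**Missing text.** Table 2 and the procedure text leading into the last marketplace condition are absent from the copy reviewed. A reader might infer that the plan never defines its counterbalancing scheme. The documents do not support that, because both the scheme and a position term could sit in the absent text. The closing model sentence is also not a full model equation. What can be said is that no visible statement includes position.

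**Remedy.** A reader might infer that position belongs in every model, or that the separate per-dose tests should give way to contrasts from one pooled model. Neither follows. If order is balanced only across participants, fitting position in separate 30-person models costs 1.0 point (four conditions), 1.3 points (b, c, d) and 3.3 points (a versus d, 90.0% to 86.7%) when there is no drift. Pooled contrasts assume a common residual variance and a common position effect over doses from 0.4 to 17.4 mg/g. A common term would not remove drift that differs by dose. This part of the objection stands.

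**Precision of the figures.** The two-condition loss depends on which labels form the pair: at 0.3 SD, power ranges over about 82 to 89%. The comparisons a versus c and c versus d were not computed. The results should be read as ranges.

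**Conclusion.** The point holds as a cheap, minor improvement. The visible Aim 2 models leave session position out, so shared drift would lower precision in analyses 2 to 5 and in the dose-by-condition interaction. Analysis 1 lies within one session and is unaffected. The loss is negligible below about 0.1 within-subject SD per session, about 1 to 4 points at 0.2 SD and about 3 to 7.5 points at 0.3 SD. This rests on linear drift common to participants, ρ = 0.5, sphericity and Williams-type orders.

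A reader might infer something stronger: that condition effects are confounded with order, that false positives rise, or that 30 per dose is too few. The documents support none of these. Counterbalancing guards against systematic bias, although uneven sequence counts can leave a small chance imbalance in a particular allocation. Type I error stays near 5% or falls below it. The stated sample size reproduces.

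**What to change.** In the across-dose mixed models that compare conditions (analyses 2 to 5), pre-specify session position (1 to 4) as a categorical fixed effect. Use one set of three coefficients common to all doses, and do not subject it to the covariate significance screen.

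The separate per-dose tests may stay as planned. Add position to them only if order was balanced within dose, where it costs 0.1 to 0.2 point without drift. Within-dose contrasts from the across-dose model are an optional alternative if a common residual variance and position effect are acceptable. If Table 2 or the procedure text already specifies a position term, no change is needed.

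Cost: a sentence in the analysis plan and three degrees of freedom; session number is already known. With no drift, the across-dose model loses 0 to 0.6 power point for the dose interactions and 0 to 0.4 point for within-dose contrasts. The gain begins at about 0.1 SD per session. Leave analysis 1, Experiment 1 and the covariate screen as they are.
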